1.3 Number of subjects

The original plan was to recruit approximately 350 subjects, stratified by current line of treatment (2nd/3rd line plus) and ethnicity (Asian/non-Asian), randomized in a 1:1 ratio to the treatments as specified below:

- AZD9291 80mg QD
- AZD9291 80mg QD and MEDI4736 10mg/kg q2w

The study was terminated early with only 29 patients randomized. This number is not considered sufficient for statistical comparison of the treatment groups, and all data reporting will be using summaries and listings.

2. ANALYSIS SETS

2.1 Definition of analysis sets

These analysis sets apply only to the primary summary. The final summary will include only data collected between the primary summary data cut-off and the time when last patient receiving MEDI4736 reaches the end of safety follow up.

2.1.1 Full Analysis Set

The Full Analysis Set (FAS) will include all randomized subjects. The FAS will be used for all efficacy summaries and treatment groups will be presented on the basis of randomized treatment, regardless of the treatment actually received.

2.1.2 Safety Analysis Set

The Safety Analysis Set will consist of all subjects who received at least one dose of randomized treatment. Safety data will be summarized using the Safety Analysis Set, according to the treatment that patients received in their first cycle. Patients who received at least one dose of MEDI4736 in the first treatment cycle (15 +/-3 days) will be regarded as being in the combination treatment. Additional summaries might be provided for the patients who were randomised and received the combination but later discontinued MEDI4736 as appropriate.

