2.2 Violations and deviations

All important deviations related to the study inclusion or exclusion criteria and study conduct will be listed and summarised by randomized treatment group. None of the deviations will lead to any subjects being excluded from any of the analysis sets described in Section 2.1 (with the exception of the PK Analysis Set, if the deviation is considered to impact upon PK respectively).

The following general categories will be considered important deviations. This list is not exhaustive and additional important deviations may be added prior to database lock. A full list is provided within the study Protocol Deviations documentation.

- Informed consent procedure deviation (e.g., no informed consent signed prior to any screening procedure)
- Eligibility criteria deviation (e.g., any inclusion criteria not met or exclusion criteria met)
- Prohibited medication deviation (e.g., subject received other anticancer agents, investigational agents, or radiotherapy while on study treatment)

The categorization of these as important deviations is not automatic and will depend on duration and the perceived effect on efficacy.

In addition to the programmatic determination of the deviations above, monitoring notes or summaries will be reviewed by the clinical team to determine any important post-entry deviations that are not identifiable via programming, and to check that those identified via programming are correctly classified. The final classification will be made prior to database lock.

Incorrect stratifications will be summarized and listed, separately to the important protocol deviations. For this, a comparison will be made between the stratification factors entered into Interactive Voice Response System (IVRS) vs. the electronic case report form (eCRF) data.

A summary will be produced showing any subjects who received a treatment different to that assigned by the randomization for any duration of treatment (for example if a subject randomized to AZD9291 monotherapy but did receive at least one dose of MEDI4736). Note, this is not due to tolerability issues where subjects experience a drug interruption and/or drug delay.

Subjects who receive the wrong treatment at any time will be included in the Safety Analysis Set as described in Section 2.1.2. During the study, decisions on how to handle these situations will be made on an individual basis with written instruction from the study team leader/physician and/or statistician.

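### The safety column is fixed by first-cycle treatment, so adverse events after a MEDI4736 dose first given later would be tabulated under AZD9291 monotherapy

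*SAP*

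**What the plan says.** SAP section 2.1.2 summarises safety data "according to the treatment that patients received in their first cycle". The combination side is spelled out: "Patients who received at least one dose of MEDI4736 in the first treatment cycle (15 +/-3 days) will be regarded as being in the combination" group. The monotherapy side is left to follow from the first of these statements. The only further provision there is optional and concerns patients who stopped the drug: "Additional summaries might be provided for the patients who were randomised and received the combination but later discontinued MEDI4736 as appropriate".

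Section 2.2 plans a summary of patients who received something other than their assigned treatment, "for example if a subject randomized to AZD9291 monotherapy but did receive at least one dose of MEDI4736", and adds "Note, this is not due to tolerability issues where subjects experience a drug interruption and/or drug delay". It then returns these patients to the same rule: "Subjects who receive the wrong treatment at any time will be included in the Safety Analysis Set as described in Section 2.1.2". Handling is otherwise left to individual written decisions, and no column rule is given for them.

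Section 3.3.1 brings adverse events into the summaries up to 30 days after AZD9291 and 90 days after MEDI4736. Section 2.1 limits these analysis sets to the primary summary, which section 1.2 says is the one used for the CSR. The final summary uses Groups A and B instead.

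**The concern.** The primary objective in section 1.1 is the safety and tolerability of the combination, and single-agent AZD9291 safety is an exploratory objective. The safety tables should therefore separate events that occurred under MEDI4736 exposure from those that did not. A column fixed in cycle 1 fails to do so for a patient whose first MEDI4736 dose falls after the stated 15 +/-3 days. That could be a combination patient with a delayed first infusion, or a monotherapy patient given MEDI4736 in error later on.

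If such a patient exists, events after MEDI4736 are missing from the column that the primary objective concerns and appear in the column meant to describe AZD9291 alone. Section 1.2 says enrolment stopped because of interstitial lung disease-like events with this combination in another study, so even one event in the wrong column could be misread.

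**Working it through.** **Tracing the rule.**

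1. A patient whose first MEDI4736 dose comes after cycle 1 received only AZD9291 in cycle 1. Under section 2.1.2 the patient is not combination, and by implication is monotherapy.
2. Section 3.3.1 still includes this patient's events during MEDI4736 and for 90 days after it. They are therefore tabulated, under monotherapy.
3. No other provision moves the patient. The optional summaries in 2.1.2 cover patients who discontinued MEDI4736, not late starters. Section 2.2 refers back to 2.1.2. Section 4.2.8.1 tabulates grades by actual treatment group but does not define that term differently.

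**Inputs for the size.** The SAP has no figure of its own to reproduce.

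- 29 patients randomised, 1:1 (section 1.3). Arm sizes are not given; I assume 15/14 or 14/15, all treated.
- Number of late starters, k: not given. Assumed range 0 to 2.
- Event counts: assumed, for illustration only.

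**Late starters randomised to the combination, each with the event.** Let c and m be the patients randomised to combination and monotherapy, and x the events among other combination patients, with none in other monotherapy patients.

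- Any-dose rule: combination (x + k)/c, monotherapy 0/m.
- First-cycle rule: combination x/(c − k), monotherapy k/(m + k).

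| c / m | k | x | Any-dose rule: comb. vs mono. | First-cycle rule: comb. vs mono. |
|---|---|---|---|---|
| either | 0 | any | no change | no change |
| 15 / 14 | 1 | 0 | 1/15 = 6.7% vs 0/14 | 0/14 vs 1/15 = 6.7% |
| 14 / 15 | 1 | 0 | 1/14 = 7.1% vs 0/15 | 0/13 vs 1/16 = 6.25% |
| 14 / 15 | 1 | 1 | 2/14 = 14.3% vs 0/15 | 1/13 = 7.7% vs 1/16 = 6.25% |
| 15 / 14 | 1 | 2 | 3/15 = 20.0% vs 0/14 | 2/14 = 14.3% vs 1/15 = 6.7% |
| 15 / 14 | 2 | 0 | 2/15 = 13.3% vs 0/14 | 0/13 vs 2/16 = 12.5% |
| 14 / 15 | 2 | 0 | 2/14 = 14.3% vs 0/15 | 0/12 vs 2/17 = 11.8% |

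In the fourth row the difference between columns falls from 14.3 points to 7.7 − 6.25 = about 1.4 points.

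**Monotherapy patient later given MEDI4736, with the event, no other events.**

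- Split 15/14: first-cycle rule 0/15 vs 1/14 = 7.1%; any-dose rule 1/16 = 6.25% vs 0/13.
- Split 14/15: first-cycle rule 0/14 vs 1/15 = 6.7%; any-dose rule 1/15 = 6.7% vs 0/14.

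**Late starter without the event.** With c = 14, m = 15 and two events in other combination patients, the any-dose rule gives 2/14 = 14.3% vs 0/15. The first-cycle rule gives 2/13 = 15.4% vs 0/16. The combination rate rises by about 1.1 points.

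**The case against.** The strongest reply is that nothing is shown to have gone wrong. The SAP does not say that any of the 29 patients started MEDI4736 after cycle 1 or received it in error; section 2.2 gives that case only as an example. If there is no such patient, no table changes. This stands, and it makes the point conditional.

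A reader might infer that the rule systematically hides combination toxicity. The SAP does not support that. The signal is diluted only if the late starter has an event after MEDI4736. An event-free late starter raises the combination rate, and events before a late first infusion are correctly placed under monotherapy by the present rule.

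The alternative is also imperfect. Defining the column by later exposure moves AZD9291-only events into the combination, possibly including an event that caused the delay. This stands too, and is why those events need marking in the tables themselves.

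Visibility is better than the tables alone suggest. Section 4.1 presents primary-summary listings by randomised group, so a combination patient with a delayed infusion would be listed under combination. The section 2.2 summary would show a monotherapy patient given MEDI4736 in error, and section 4.2.8.1 lists all adverse events with onset dates. But a tolerability-related delay falls outside the section 2.2 summary, a monotherapy patient given MEDI4736 in error is listed under monotherapy, and none of this corrects the tabulated rates.

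Finally, reporting is descriptive, without hypothesis tests (section 4), and section 1.3 calls the numbers insufficient for comparison. That limits the inferential harm. It does not justify counting events after MEDI4736 exposure as monotherapy events.

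**Conclusion.** The point holds as a conditional defect in the primary summary. Section 2.1.2 states a rule that gives the wrong column for events after a first MEDI4736 dose given later than cycle 1, and nothing elsewhere in the SAP repairs it. For one late starter with a MEDI4736-type event, about 6 to 7 percentage points move from combination to monotherapy; for two, about 12 to 14. With no late starter the effect is zero, and with an event-free late starter it is small and in the other direction.

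These sizes rest on an assumed split of 14 to 15 patients per arm, all treated, and on assumed event counts. The monotherapy assignment is implied rather than written out. It would go too far to say that toxicity has been misplaced or that the bias always favours the combination. The final summary is not affected. The change is worth making because the rule concerns the primary objective, the arms are very small and the cost is low.

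**What to change.** In section 2.1.2, replace the first-cycle criterion for the primary summary: every patient with any MEDI4736 dose, at whatever time, goes in the combination column, and all other treated patients go in the monotherapy column. Let the cross-reference in section 2.2 point to this rule, so that the column is fixed in advance and not by individual decision.

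Add that adverse events with onset before the first MEDI4736 dose are identified by a footnote or a separate row in the tables, as well as flagged in the listings, so that AZD9291-only events are not read as combination toxicity.

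The cost is a few sentences and one derived flag comparing adverse event onset with the first MEDI4736 dose date; no new data are needed. The downside is that a few AZD9291-only events sit under the combination column, visibly marked. If there are no late starters, column membership does not change.

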2.1.3 PK Analysis Set

Patients in the FAS who have at least one measurable PK concentration, supported by the relevant date and time of this sample, and for each time a PK sample was taken the dosing data for that day, and for samples taken after multiple dosing the dosing data for the 2 days prior to the sample day as well as the sample day. For any individual sample to be included in the PK Analysis Set the full sample data and dosing data needs to be present for that sample.

Table 1 below shows the analysis set to be used for each outcome variable.

Table 1 Summary of outcome variables and analysis populations

Outcome variable	Populations
Demography	Safety
Efficacy Data	FAS
	PFS
	ORR
	DoR
	DCR
	Tumor shrinkage
	OS
PK data	PK
	Plasma concentrations
	Metabolites
Pharmacodynamics and immunogenicity	Safety
	ADA
Safety Data	Safety
	Adverse Event (AE)
	Laboratory data
	Vital signs
	ECG
	Left ventricular ejection fraction (LVEF)
	World Health Organization (WHO) performance status

2.2 Violations and deviations

All important deviations related to the study inclusion or exclusion criteria and study conduct will be listed and summarised by randomized treatment group. None of the deviations will lead to any subjects being excluded from any of the analysis sets described in Section 2.1 (with the exception of the PK Analysis Set, if the deviation is considered to impact upon PK respectively).

The following general categories will be considered important deviations. This list is not exhaustive and additional important deviations may be added prior to database lock. A full list is provided within the study Protocol Deviations documentation.

- Informed consent procedure deviation (e.g., no informed consent signed prior to any screening procedure)
- Eligibility criteria deviation (e.g., any inclusion criteria not met or exclusion criteria met)
- Prohibited medication deviation (e.g., subject received other anticancer agents, investigational agents, or radiotherapy while on study treatment)

The categorization of these as important deviations is not automatic and will depend on duration and the perceived effect on efficacy.

In addition to the programmatic determination of the deviations above, monitoring notes or summaries will be reviewed by the clinical team to determine any important post-entry deviations that are not identifiable via programming, and to check that those identified via programming are correctly classified. The final classification will be made prior to database lock.

Incorrect stratifications will be summarized and listed, separately to the important protocol deviations. For this, a comparison will be made between the stratification factors entered into Interactive Voice Response System (IVRS) vs. the electronic case report form (eCRF) data.

A summary will be produced showing any subjects who received a treatment different to that assigned by the randomization for any duration of treatment (for example if a subject randomized to AZD9291 monotherapy but did receive at least one dose of MEDI4736). Note, this is not due to tolerability issues where subjects experience a drug interruption and/or drug delay.

Subjects who receive the wrong treatment at any time will be included in the Safety Analysis Set as described in Section 2.1.2. During the study, decisions on how to handle these situations will be made on an individual basis with written instruction from the study team leader/physician and/or statistician.

3. PRIMARY AND EXPLORATORY VARIABLES

3.1 Derivation of RECIST visit responses

All RECIST assessments, whether scheduled or unscheduled, will be included in the calculations. This is also regardless of whether a patient discontinues study drug.

For all patients, the RECIST version 1.1 (see further Appendix C of the CSP) tumour response data will be used to determine each patient's visit response. It will also be used to determine if and when a patient has progressed and also their best overall response.

The baseline tumour assessment is part of the screening procedures and should be performed within 28 days before the start of study treatment.

Prior to approval of CSP version 2.0, efficacy for all patients will be assessed by objective tumour assessments every 8 weeks (relative to the first dose) for the first 48 weeks, then every 12 weeks thereafter, until confirmed objective disease progression as defined by RECIST 1.1 (irrespective of the reason for stopping study drug and/or subsequent therapy). For patients who discontinue study drug due to toxicity or a reason other than confirmed progression of disease (PD), objective tumour assessments should be continued every 8 weeks for 48 weeks (relative to first dose) then every 12 weeks thereafter until confirmed objective disease

progression. If an unscheduled assessment is performed, and the patient has not progressed, every attempt should be made to perform the subsequent assessments at their scheduled visits. Patients on monotherapy AZD9291 will be assessed according to local practice until objective disease progression.

Disease progression requires confirmation, the confirmatory scan should occur preferably at the next scheduled visit and no earlier than 4 weeks after the initial assessment of PD in the absence of clinically significant deterioration. Study treatment will continue between the initial assessment of progression and confirmation for progression.

Progression would be considered confirmed if the following criteria are met:

- $\geq 20\%$ increase in the sum diameters of target lesions (TLs) compared with the nadir at 2 consecutive visits with an absolute increase of at least 5 mm.

The assessment of progression of $\geq 20\%$ increase in the sum diameters of TLs compared with the nadir is at the first progression time point relative to the nadir (the smallest sum of diameters and this may be at baseline or subsequent follow-up visit). The confirmed scan confirms the persistence of the $\geq 20\%$ increase relative to the nadir.

- And/or significant progression (worsening) of non target lesions (NTLs) or new lesions at the confirmatory PD time point compared with the first time point where progression of NTLs or new lesions identified.
- And/or additional new unequivocal lesions at the confirmatory PD time point compared with the first time point new lesions identified.

Patients who discontinue treatment for reasons other than progression would undergo a 3-month follow-up. Progressions occurring during this follow-up will not necessarily have a second confirmatory scan.

Following approval of CSP version 2.0, objective tumour assessments every 8 or 12 weeks will only be carried out for Group B patients up to disease progression or up to 3 months following treatment discontinuation, and confirmation of progression will only be required for Group B patients who continue to receive MEDI4736 following progression, while patients discontinuing treatment may not have scans to confirm progression. Following approval of CSP version 2.0, patients in Group A will not have tumour assessment scans.

RECIST 1.1 without confirmation of progression will be regarded as primary in terms of the efficacy reporting. A sensitivity summary requiring confirmation will be conducted. The confirmation should occur at least 28 days from the first scan documenting radiological progression.

At each visit for the site investigator data, an overall visit response will be programmatically determined - using the information from TLs, NTLs and new lesions.

RECIST outcomes (i.e., PFS and ORR etc) will be calculated using a computer program for site investigator data.

RECIST results based on blinded independent central review were planned in the original protocol, but were not included in version 2.0 of the protocol, and no such review was performed.

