3.2.1 Progression free survival landmark summary

The endpoint PFS, as assessed by the investigator, using RECIST 1.1 will be reported both with and without **confirmation of progression**. will be defined as the time from the date of randomisation until the date of the first objective disease progression or death (by any cause in the absence of progression) regardless of whether the patient withdraws from randomised therapy or receives another anti-cancer therapy prior to progression (i.e., date of PFS event or censoring – date of randomisation + 1).

Patients who have not progressed or died at the time of summary will be censored at the time of the latest date of assessment from their last evaluable RECIST 1.1 assessment. However, if

the patient progresses or dies after 2 or more missed visits, the patient will be censored at the time of the latest evaluable RECIST 1.1 assessment prior to the two missed visits with the exception of 2 missed visits from baseline (i.e. if the subject dies within 119 days of the last evaluable visit), the event of death will be used in the PFS summary).

Given the scheduled visit assessment scheme (i.e. eight-weekly for the first 48 weeks then twelve-weekly thereafter) the definition of 2 missed visits will change. If the previous RECIST assessment is less than study day 232 (i.e. week 32 + 7 day visit window) then two missing visits will equate to 17 weeks (2 x 8 week scans + 7 day visit window) since the previous RECIST assessment, allowing for late visits.

If the two missed visits occur over the period when the scheduled frequency of RECIST assessments changes from eight-weekly to twelve-weekly this will equate to 21 weeks. The time period for the previous RECIST assessment will be from study day 287. From week 49 (week 48 + 7 days) onwards, two missing visits will equate to 25 weeks (2 x 12 week scans + 7 day visit window).

If the patient has no evaluable visits or does not have baseline data they will be censored at baseline unless they die within 112 days of baseline (2 x 8 week scans).

The PFS time will always be derived based on scan/assessment dates not visit dates.

RECIST 1.1 assessments/scans contributing towards a particular visit may be performed on different dates. The following rules will be applied:

- For investigational assessments, the date of progression will be determined based on the earliest of the RECIST assessment/scan dates of the component that indicates progression

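### The PFS missed-visit limits assume 8/12-weekly scans for the whole FAS, although two undated sentences in Section 3.1 say otherwise and Group A study scanning stops under version 2.0

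*SAP*

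**What the plan says.** SAP Section 3.1 describes scanning in several places.

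- Schedule before version 2.0 took effect: "efficacy for all patients will be assessed by objective tumour assessments every 8 weeks (relative to the first dose) for the first 48 weeks". After week 48 the interval is 12 weeks, and scanning runs until progression is confirmed.
- Same paragraph, for patients who stop drug without confirmed progression: "objective tumour assessments should be continued every 8 weeks for 48 weeks (relative to first dose) then every 12 weeks thereafter", again until progression is confirmed.
- Same paragraph, with no date and no interval: "Patients on monotherapy AZD9291 will be assessed according to local practice until objective disease progression".
- Later in the section, also undated: "Patients who discontinue treatment for reasons other than progression would undergo a 3-month follow-up".
- After version 2.0: "objective tumour assessments every 8 or 12 weeks will only be carried out for Group B patients up to disease progression", or for up to 3 months after stopping treatment. For the others: "Following approval of CSP version 2.0, patients in Group A will not have tumour assessment scans". Section 3.2 adds that Group A tumour data are then not collected.

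Section 3.2.1 censors a progression or death that follows two or more missed visits at the last evaluable assessment before them. It sets the limits from one schedule: "Given the scheduled visit assessment scheme (i.e. eight-weekly for the first 48 weeks then twelve-weekly thereafter) the definition of 2 missed visits will change". They are 17, 21 or 25 weeks, depending on when the previous scan was done. No exception is made by arm, group or protocol version. PFS is summarised on the FAS, and DoR takes its event and censoring dates from PFS (Sections 2.1.1 and 3.2.3).

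**The concern.** A missed-visit rule needs a planned visit to miss. The limits in Section 3.2.1 are elapsed times that represent two missed visits only for a patient on the 8/12-weekly schedule. For a patient whose study scanning has stopped by plan, no visit is missed, yet the limits still decide which deaths count.

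Such a patient contributes PFS time beyond the last scan only by dying. A death within the limit is an event at the date of death. Progression cannot be recorded, and a patient without an event is censored at the last scan. Some of this is present in any scan-based PFS, but under scheduled scanning the next scan brings survivors back into follow-up. Once scanning has stopped, that does not happen.

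If local-practice scanning applied before version 2.0, there is a second effect: a recorded progression could be censored although no planned scan was missed. At stake are the Kaplan-Meier curves, APF6, APF12 and DoR.

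**Working it through.** **1. The plan's limits reproduce from one schedule only.** Scans fall at weeks 8, 16, ..., 48, 60, 72, and so on. Each limit is the time to the second next scan plus 7 days.

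- Both next scans 8-weekly: 2 × 8 + 1 = 17 weeks = 119 days.
- One of each: 8 + 12 + 1 = 21 weeks = 147 days.
- Both 12-weekly: 2 × 12 + 1 = 25 weeks = 175 days.
- First threshold, week 32 plus 7 days: 32 × 7 + 7 + 1 = study day 232.

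The plan's figures are therefore correct for 8/12-weekly scanning. No other schedule in the SAP yields them.

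**2. The two undated sentences.**

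- Local practice: if it applies before version 2.0, it conflicts with 8/12-weekly scans for all patients. If it applies after, it conflicts with no scans for Group A, unless that means no study scans.
- 3-month follow-up: if it applies before version 2.0, it conflicts with scanning until progression is confirmed. If it applies after, it agrees with the version 2.0 rule for Group B.

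**3. Group A after study scanning stops, last scan before day 232.**

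- Dies up to 119 days after the last scan: event at death.
- Dies later: censored at the last scan.
- Progresses at any time: not recorded.
- Remains alive: censored at the last scan.

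**4. Local practice before version 2.0.** The SAP gives no interval, so these are assumptions. With the last scan before day 232, the scan after k missed scans comes at (k + 1) × interval, and a progression there is censored if that exceeds 17 weeks.

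| Assumed interval (weeks) | Missed scans needed for censoring | Gap (weeks) |
|---|---|---|
| 6 | 2 | 18 |
| 8 | 2 | 24 |
| 9 | 1 | 18 |
| 12 | 1 | 24 |
| 16 | 1 | 32 |
| 18 | 0 | 18 (126 days, against 119) |

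The rule works as intended at 6 to 8 weeks, is stricter at 9 to 16 weeks, and censors with nothing missed at 18 weeks or more.

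**5. Size of one event.** A Kaplan-Meier step is S(t−)/n, where n is the number at risk. The SAP gives 29 randomised 1:1, so about 14 per arm is assumed.

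- 14 at risk, S = 1: 1/14 = 7 points.
- 7 at risk, all earlier exits events: S = 7/14 = 0.5, and 0.5/7 = 7 points.
- 5 at risk, all earlier exits events: S = 5/14, and (5/14)/5 = 7 points.
- 7 or 5 at risk, all earlier exits censored: 1/7 = 14 points and 1/5 = 20 points.

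The step thus lies between 1/14 and 1/n.

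**6. Reach to the landmarks.** Section 4.1 sets a month at 30.4375 days, so 6 months is 182.6 days and 12 months is 365.25 days. A last scan by day 231 plus 119 days reaches day 350, so the 17-week limit can bear on both landmarks. The 25-week limit needs a last scan from week 49: 48 × 7 + 7 + 1 = day 344. It cannot affect APF6, and it affects APF12 only through deaths in about 365 − 344 = 21 days.

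**The case against.** The strongest reply is that much of Section 3.1 is a dated sequence: 8/12-weekly for all before version 2.0, then Group B only. The local-practice sentence fits Section 1.2, where Group A follows the usual approach of the site, and the 3-month sentence fits the version 2.0 rule beside it. If local practice applied only after version 2.0, those scans are not collected and no progression seen on them can be wrongly censored. Exposure is also narrow: Section 1.2 defines Group A by treatment continuing after the primary cut-off, and the final summary reports efficacy for Group B only.

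Most of this limits the size of the problem. A reader might infer that Section 3.1 contains three mutually incompatible schedules. It does not: stopping Group A scans after version 2.0 does not contradict scanning before it. The 18-week example is conditional for the same reason.

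Two things remain. The two sentences carry no date, so the favourable reading must be supplied by the reader. And on any reading, Section 3.2.1 makes no exception once study scanning stops. This can reach the primary summary: the cut-off follows approval in the last country with active patients, reduced Group A collection starts at each site's approval, and Section 1.2 itself warns of sparse data in that summary.

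**Conclusion.** The point holds as a lower-severity correction. Section 3.1 has two undated sentences that conflict with the schedule before version 2.0. Section 3.2.1 applies limits valid only for 8/12-weekly scans to patients who may not be on that schedule. For Group A patients at early-approved sites, whether PFS time runs past the last scan depends on whether the patient dies.

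One reclassified event is worth about 7 points in an arm of about 14 with little earlier censoring. A reader might take 14 to 20 points as the typical effect, but that is a ceiling, reached with 5 to 7 at risk only if earlier exits were nearly all censored. Nor does the 175-day limit distort APF12 broadly; it can act only in the last three weeks or so before that landmark.

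A reader might also infer a known bias between arms. The SAP does not support one: Group A includes combination-arm patients who stopped MEDI4736, and no approval dates, at-risk numbers or local-practice intervals are given. Efficacy is exploratory, 29 patients are judged too few for comparison, and no hypothesis is tested. The effect is on descriptive APF6, APF12, the curves and DoR.

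**What to change.** - Reconcile Sections 3.1 and 3.2.1 into one statement of which scan schedule applied to which patients and when, including follow-up after stopping treatment without progression. Which schedule applied is for the sponsor to state.
- In Section 3.2.1, apply the 17-, 21- and 25-week limits only while scheduled scanning was in force for that patient.
- For patients whose study scanning stopped under version 2.0, censor PFS and DoR at the last evaluable scan on or before the date it stopped. Keep scheduled Group B data in the main summary; cutting both arms off at version 2.0 would discard validly scheduled scans and is not needed.
- Add a supportive PFS that counts every recorded progression or death regardless of missed visits.

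The cost is SAP wording, the date on which study scanning stopped for each patient (from site approval of version 2.0) and one extra output. The downside is that a few deaths after scanning stopped move from the main PFS output to the supportive one.
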